#### **3.6.2 Procedures**

##### **Screening**

All patients attending the endocrinology outpatient service of the Hospital Arzobispo Loayza will be invited to participate in an initial assessment to determine if they are eligible to participate in the study. This assessment consists of: (1) verifying if the participant is overweight, obese or severely obese (but not morbidly obese), (2) confirming that they have someone in their close social circle (family or friends) who are of legal age and healthy and would be willing to fulfill the role of "companion" which consists of supporting them throughout the pilot study in order to reach their weight loss goals, (3) confirming that their diabetes treatment consists of Metformin or dietary changes. Those patients who meet the inclusion criteria will be invited to participate in the study and once they accept, a blood sample will be collected to document their baseline HbA1c levels.

## **Phase 1: Baseline**

Baseline information will be collected including demographic data, socioeconomic status, relevant background information such as time since diagnosis, type of antidiabetic drugs, lifestyle (smoking, alcohol consumption and physical activity), depression, presence of diabetes complications and comorbidities (See Annex 1). Anthropometric measurements such as weight, height and blood pressure, and blood tests such as glycated hemoglobin (HbA1c) will also be included.

## **Phase 2: Intervention**

The patient will be contacted within three days of signing the consent form and their participation will be confirmed. Then the participants will be randomized. Those participants in intervention group 1 should not bring their companion to any of the meetings while in the case of intervention 2 and 3, the companions should sign a commitment to support the patient during the weight loss plan and to share the reward.

Subsequently, all selected patients will fill out the "Personality Inventory" survey to collect data on non-cognitive skills. (See Annex 6).

## **Phase 3: Weight loss follow-up**

The follow-up will be carried out by a professional person qualified as a Diabetes Educator who will be trained by the project staff to follow up the 45 patients and their companions.

### **Arm1: Individual Incentives**

Participants will be required to come every 2 weeks to measure their weight and to collect a blood sample for glucose measurement with a glucometer. Weight will be measured in fasting conditions, using the same scale and at the same time as the previous visit.

Each participant will attend a total of 8 sessions (including the initial meeting). In sessions 2 to 7 the diabetes educator will weigh them to see if they reached the goal.

- ***If they reached the goal:*** They will be rewarded and asked about the actions taken to reach their goal. In addition, suggestions for improving their nutrition and diabetes management will be reviewed. For this purpose, the information entered by the participants in their diary will be used. They will also be asked about their physical activity, adherence to treatment and changes in their eating habits. If they have received a reward in the previous session, they will be asked about how they used that reward.

- **If they did not reach the goal:** They will be asked about the actions they took to lose weight and the main challenges in implementing them. For this purpose, the information entered by the participants in their diary will be used. Suggestions for improving their nutrition and diabetes management will be reviewed. They will also be asked about their physical activity, adherence to treatment and changes in their eating habits.
- The patient will fill out a diabetes self-management questionnaire at each session (See Annex 4).

In session 7, a blood sample will be collected to measure his/her Hba1c. The results will be given in session 8 (last session) in which he/she will be rewarded if his/her Hba1c has dropped at least 1% since the beginning of the study (See Annex 7).

### **Arm 2: Mixed Incentives: Set up by Researchers**

Participants will be asked to come for a weight measurement every 2 weeks and for the collection of a blood sample to measure glucose with a glucometer, if possible, together with their companions. Each pair (patient and companion) will attend a total of 8 sessions. The reward is conditional on the presence of the companion. In sessions 2 to 7 they will be weighed by the diabetes educator.

- **If they reached the goal:** The patient and the companion (if present) will be rewarded. If the companion is not at the meeting, the nurse will contact him/her by phone to coordinate the date and time when he/she can come to receive his/her part of the reward. The patient and the companion will be asked about the actions taken to reach their goal. In addition, suggestions for improving nutrition and diabetes management will be reviewed. For this purpose, the information entered by the participants in their diary will be used and a short questionnaire oriented to self-report adherence, physical activity and dietary changes will be administered. In case of having received a reward in the previous session, they will be asked about how they used it.
- **If they did not reach the goal:** They will be asked about the actions taken to lose weight and the main challenges to implement them. For this purpose, the information entered by the participants in their diary will be used. Suggestions for improving nutrition and diabetes management will be reviewed. In addition, a short questionnaire oriented to self-report adherence will be administered. In session 7, a blood sample will be collected to measure his/her Hba1c. The results will be given in session 8 (last session) in which he/she will be rewarded if his/her Hba1c has dropped at least 1% since the beginning of the study, and if

his/her companion has been with him/her.

### **Arm 3: Mixed Incentives: Set up by Participants**

Participants will be required to visit every 2 weeks, if possible with their companions, to measure their weight and to collect a blood sample for glucose measurement using a glucometer. Each pair (patient and companion) will attend a total of 8 sessions. In sessions 2 to 7 the diabetes educator will weigh them.

- ***If they reach the goal:*** The patient and the companion should negotiate, based on the effort perceived by each of the parties, what percentage of the reward corresponds to each one, with the condition that the maximum percentage to be received is 80% and the minimum is 20%. The patient and the companion (if present) will be rewarded. If the companion is not at the meeting, the negotiation will take place by telephone and then the nurse will call him/her to coordinate the date and time when he/she can come to receive his/her part of the reward. The patient and the companion will be asked about the actions taken to reach their goal. In addition, suggestions for improving nutrition and diabetes management will be reviewed. For this purpose, the information entered by the participants in their diary will be used and a short questionnaire oriented to self-report adherence, physical activity and dietary changes will be administered.
- ***If they did not reach the goal:*** They will be asked about the actions taken to lose weight and the main challenges to implement them. For this purpose, the information entered by the participants in their diary will be used. Suggestions for improving nutrition and diabetes management will be reviewed. In addition, a short questionnaire oriented to self-report adherence, physical activity and dietary changes will be administered.
- In session 7 a blood sample will be collected to measure his/her Hba1c. The results will be given in session 8 (last session) in which he/she will be rewarded if his/her Hba1c has dropped at least 1% since the beginning of the study, and if his/her companion has been with him/her.

### **Phase 3: Follow-up of experiences with the research study**

In-depth interviews will be used with study participants. To (a) explore their opinion about the impact of having received financial incentives to lose weight and thus improve their diabetes management; (b) explore their opinion about the amount of the incentive, to find out if it was considered high, very low or reasonable, (c) find out their opinions about the educational material received (d) find out (in arm 2) the role played by the companions and document the different ways in which they supported the patient to reach his/her goals.

**Procedures:** Interviews will be conducted by personnel appropriately trained in qualitative techniques. Interviews will be audio-recorded and transcribed verbatim. Transcripts will be coded according to themes using ATLAS.ti version 7 for Windows.

**Sample size:** 30 people.

- 18 participants; 6 from the individual incentive arm, 6 from the researcher-determined mixed incentive arm, and 6 from the participant-determined mixed incentive arm.
- 12 companions: 6 from each arm.

### 3.7. Communicating results to patients

HbA1c, blood pressure, and weight results will be communicated and given to participants by the diabetes educator of the study. Participants will be advised, if necessary, to consult their attending physician for proper interpretation of the results.

### 3.8. Timeline

Research activities	MONTHS									
	1	2	3	4	5	6	7	8	9	10
Protocol preparation	x									
Ethics approval		x	x							
Recruitment				x	x					
Intervention					x	x	x	x		
Qualitative assessment								x	x	
Interview transcription									x	
Data analysis						x	x	x		
Final report writing										x

## **4. PROTECTION OF HUMAN SUBJECTS**

### **4.7. Ethics**

This protocol, questionnaires and informed consents - and any subsequent modifications - will be reviewed and approved by the Comité Institucional de Ética - CIE (Institutional Ethics Committee) of the Hospital Nacional Arzobispo Loayza with regard to their scientific content and compliance related to research on human subjects.

### **4.8. Informed Consent**

Before providing informed consent, participants will be given the opportunity to ask questions until they fully understand the study. The interviewer will sign the guide to informed consent and give a copy to the interviewee (See Annex 4).

All participants will be assigned a unique identification code. Data will be stored in paper and electronic form. Electronic data will be archived, copied and secured with passwords. Paper forms will be stored in locked cabinets with access limited to specific individuals. Personal information, including the participant's name, address, date of birth, and other potential identifiers will be stored in password-protected folders. Only study staff will have access to this information.

### **4.9. Benefits**

Participants may benefit from the financial incentives they receive and from the education and medical test results provided during their participation. This research study is subsequently for the participant to use the incentives for improvement and control of his/her disease.

#### **4.10. Risks**

No major security issues are expected in this study. Transportation costs, if necessary, will be covered by the project.

#### **4.11. Payment to participants**

Participants will not receive payment for participating in this study. They will receive a financial incentive for reaching certain weight loss and diabetes management goals.

#### **4.12. Confidentiality**

All information related to the study will be stored securely. All participant information will be stored in password-protected databases on computers accessible only to study investigators. All reports, study data, processes, and administrative forms will be identified only by a numeric code to maintain confidentiality. All information resulting from this research study will be treated with strict confidentiality, and only the investigators named in this study, local regulatory authorities, Ethics Committees, and those they designate will have access to this information.

Findings of this study will be submitted by the investigators to peer-reviewed indexed journals for publication.

## 5. DATA MANAGEMENT AND ANALYSIS PLAN

### 5.7. Data Security and Quality Control

A multi-faceted program for data quality control of the study that includes: (1) daily meetings and reviews with field interviewers for quality control as well as training updates, (2) duplicate data entry into a revenue-related database and that has automatic monitors for data validity, and (3) a continuous review of the statistical description of study data by the Principal Investigator is proposed.

Field visits will be conducted during the study to ensure that regulatory requirements are met. Data security includes physical security of paper-based formats and computers used for the study, as well as password protection and a backup of all information on the computers.

The close cooperation of the study investigator, field interviewers, data managers, and other members of the research team will be necessary to follow the progress of the study, answer questions about the proper execution of the study, and address other issues in a timely manner.

### 5.8. Analysis Plan

#### 5.8.1. Baseline and Follow-up

The information collected will be entered and tabulated in order to identify the participants' characteristics. Subsequently, the data will be descriptively analyzed using measures of central tendency, measures of dispersion, absolute frequencies and relative frequencies, according to the type of variable.

For longitudinal data analysis, the three arms of the study (individual incentives, mixed incentives set up by researchers, mixed incentives set up by participants) will be compared, using as outcomes the difference in weight (every 15 days for three months) and the difference in the percentage of glycated hemoglobin (at three months). For this purpose, relative risks with 95% confidence intervals will be used.

5.8.2. Qualitative Research: In-depth interviews. The interviews will be recorded in mp3, transcribed and then analyzed using Atlas-ti software. This software allows coding the interviews in order to identify common themes, frequency of opinions and explanatory details of the answers given.

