### **3.4. Sample size**

Seventy-five people (patients and companions):

- 45 patients assigned to three intervention groups, 15 in each group (see section 3.5).
- 30 companions: Since two of the groups will require a companion, 30 people will be enrolled to be with the participant throughout the intervention.

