#### *Intervention 1: Individual Incentives.*

1. Participants will receive information about the study, specifying that they will receive a reward of 150 soles (about 25% of the minimum wage) at each meeting if they have managed to lose one kilogram in a two-week period. The meetings will take place every two weeks for three months.
2. An initial assessment will be made to determine their weight and the results of their HbA1c will be provided.
3. A plan will be made to determine how many kilograms they should have at each biweekly meeting (Annex 3).
4. Education on nutrition and physical activity will be provided.

5. A manual with information on nutrition and physical activity for people with diabetes interested in losing weight will be given, including tips for loosing weight and a weight loss plan for a two-week period (Annex 4). The DE will manage an "ideal" weight loss plan for the patient throughout the 3 months of the study.
6. They will be given a diary to enter their daily diet and physical activity. The information in this diary will be the starting point to discuss with the diabetes educator at each session about the barriers and achievements in the implementation of the weight loss plan (Annex 4).
7. In addition to the introductory meeting, they will attend seven follow-up sessions (See Figure 1) and a final one in which he/she will be rewarded with the same amount (150 soles) if he/she managed to lower their HbA1c by at least 1%.

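### The fortnightly weight comparison names no within-patient method, leaves the reference point of the difference undefined, and does not carry over the three-month comparison as its main result

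*Combined protocol and SAP*

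**What the plan says.** The quantitative comparison is set out in section 5.8.1 (Baseline and Follow-up). It sets the three arms against each other, "using as outcomes the difference in weight (every 15 days for three months". HbA1c enters once, at the end of that period. The stated method for both is that "relative risks with 95% confidence intervals will be used". The label is longitudinal, but no model, covariance structure, clustered variance, main visit or multiplicity rule follows. The section does not say from which weight the difference is taken, or which pairs of arms are contrasted.

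Section 3.4 gives "45 patients assigned to three intervention groups, 15 in each group". The Arm 1 procedures say "In sessions 2 to 7 the diabetes educator will weigh them to see if they reached the goal", which is six weigh-ins after baseline; Arms 2 and 3 match.

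Two other places bear on the point:

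- Section 3.5 Outcomes describes a comparison of weight loss and HbA1c when the three months are over. It is not called primary, and 5.8.1 does not repeat it for weight.
- The session counts differ. The Arm 1 procedures say "Each participant will attend a total of 8 sessions (including the initial meeting", while Intervention 1 says "In addition to the introductory meeting, they will attend seven follow-up sessions (See Figure 1) and a final one", which read literally makes nine.

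**The concern.** A relative risk with a confidence interval compares two groups on an event recorded once per patient. Here the outcome is a weight difference recorded about six times per patient. The one fortnightly event that the protocol defines is the one-kilogram goal. To apply the stated method, the analyst must either make a separate comparison at each visit or combine visits, and the plan does not choose.

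The first route gives many intervals with none marked as the main one, so a chance difference at some visit is easy to find. The second, done without allowing for the patient, counts repeated results from 15 people as if they came from different people.

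Section 2 says the results will feed the design of a later randomized trial, and section 4.12 says they will be submitted for publication. A chance difference or a falsely narrow interval could make one incentive scheme look better than the data show.

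**Working it through.** **The plan's own figure.** Only the sample size can be reproduced: 3 × 15 = 45 patients, and 45 + 30 companions = 75. Both agree with section 3.4. The plan gives no power, standard deviation or within-patient correlation, so every error rate below rests on assumptions.

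**Step 1: how many intervals.** Count = contrasts × (weight time points + 1 for HbA1c).

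| Reading | Three pairs | One reference arm |
|---|---|---|
| Six weigh-ins (Arm procedures) | 3 × 7 = 21 | 2 × 7 = 14 |
| Seven weigh-ins (if each follow-up session in the Intervention descriptions is a weigh-in) | 3 × 8 = 24 | 2 × 8 = 16 |
| Three-month comparison only (3.5 Outcomes) | 3 × 2 = 6 | 2 × 2 = 4 |

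The text allows 4 to 24. The rest uses six weigh-ins.

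**Step 2: chance that at least one interval excludes no difference when there is none.**

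- If 21 intervals were independent: 1 − 0.95^21 = 0.66. Visits are correlated, so this is too high.
- Simulation, 15 per arm, t intervals on mean differences, weight–HbA1c correlation assumed 0.4. With an equal correlation between visits of 0.3, 0.5, 0.7 and 0.9, the rate for 21 intervals is 56%, 50%, 42% and 33%. With a random-walk pattern it is 42%.
- Simulation with assumed patient slopes of SD 0.5 kg per fortnight and visit noise of SD 0.6 kg. For the 18 weight intervals alone the rate is about 30% for change from baseline and about 51% for change since the previous visit. The undefined reference point alone therefore moves the answer by some 20 percentage points.
- Same slopes and noise, but with the plan's own measure: log relative risk with Wald limits on the one-kilogram goal. For assumed mean losses of 0.5, 0.8 and 1.0 kg per fortnight, the 18 intervals give about 27%, 45% and 48%.
- Three-month comparison only, six intervals: about 22% simulated, against 1 − 0.95^6 = 0.26 if independent.

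**Step 3: pooling visits as if independent.** Each arm contributes 15 × 6 = 90 rows. With within-patient correlation ρ, the design effect is 1 + 5ρ, and a nominal 95% interval covers 2Φ(1.96/√DE) − 1.

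| Assumed ρ | Design effect | Coverage |
|---|---|---|
| 0.08 | 1.4 | 90% |
| 0.1 | 1.5 | 89% |
| 0.3 | 2.5 | 78% to 79% |
| 0.5 | 3.5 | 70% |
| 0.7 | 4.5 | 64% |

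The slope-and-noise model of Step 2 implies ρ of about 0.08 for the fortnightly goal. In that model, the simulated error of the pooled relative risk is about 9% per contrast, or 91% coverage, close to the formula. The lower rows are separate assumptions. Correlations that high are more plausible for change from baseline than for the fortnightly goal.

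**The case against.** The strongest reply is that this is an exploratory feasibility pilot (Protocol Summary and section 3.1). Its objectives are about implementation, no passage selects a scheme because an interval excludes the null, and each per-visit interval is valid at its own visit. This stands in part: strict control of the family-wise error is not needed, and multiplicity weighs less than in a confirmatory trial. It does not excuse pooled intervals that are too narrow, and the Protocol Summary itself opens with comparing the effect of the incentive on glycated hemoglobin.

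Three stronger readings are tempting, and the documents do not support them:

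- A reader might infer that the plan commits to 21 separate intervals. It says neither that each visit is analysed separately nor that all three pairs are contrasted.
- A reader might infer that no end-of-study weight comparison is planned. Section 3.5 Outcomes describes one. The fault is that it is not named as the main result and that 5.8.1 does not carry it over.
- A reader might take coverage below 80% as the expected cost of pooling. That needs a goal correlation of about 0.3, which the documents do not give. If the difference is from the previous visit, neighbouring differences share a weigh-in whose noise enters with opposite signs. The correlation can then be low or negative, and the loss of coverage small or reversed.

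**Conclusion.** The concern holds as an under-specified and ill-matched analysis. The stated measure is applied to a repeated outcome with no within-patient method, no defined reference point for the difference and no main time point. Both ways of running it as written are worse than a standard alternative.

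The size is illustrative. Visit by visit, up to 21 intervals are possible with six weigh-ins, and the chance of at least one false exclusion is roughly 30% to 55%, depending on the assumed correlations and on how the difference is defined. Pooled as independent, coverage for the fortnightly goal is about 91% under the slope-and-noise model, and lower if the within-patient correlation is higher.

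This should be corrected before the data are analysed. It does not undermine the pilot's feasibility and qualitative aims.

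**What to change.** In section 5.8.1:

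1. Define the weight difference as change from baseline.
2. For weight, replace the relative risk with mean differences from one linear mixed model with arm, visit, arm-by-visit and baseline weight, and the patient as the repeated unit.
3. Name the between-arm difference at three months (session 7 in the numbering of the Arm procedures) as the headline weight result, in line with section 3.5 Outcomes. Show the other visits as a curve.
4. Label the pairwise intervals descriptive. A single time point still leaves three contrasts for weight and three for HbA1c, with the chance of about 22% shown above.
5. If goals reached are compared, use GEE with patient-clustered robust standard errors and a small-sample correction, since there are only 15 patients per arm. Alternatively, count each patient's goals reached out of the scheduled weigh-ins (six under the Arm procedures).
6. Reconcile the session counts in the Intervention descriptions with those in the Arm procedures, so that the number of weigh-ins is fixed.

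The cost is plan wording and a standard model, with no new patients, visits or measurements. The downside is that the headline rests on one time point and weight is no longer summarised as a relative risk.

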##### **3.3.1 Inclusion criteria for the patient**

Subjects will be eligible if

1. They have a diagnosis of type 2 diabetes mellitus,
2. They aged 18 to 70 years,
3. They receive treatment with Metformin or their treatment consists of dietary changes.
4. They have a body mass index between 25kg/m^2 to 39.9 kg/m^2 (range that includes from overweight to severe obesity),
5. They are able to consent,
6. They are not fulfilling the role of a companion in the framework of this pilot study.
7. They do not have blindness, amputations or foot ulcers nor are receiving dialysis as a consequence of diabetes mismanagement.

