### **3.6 Recruitment process**

#### **3.6.1 Randomization and other processes**

The recommendations of the CONSORT statement [26] will be followed in the randomization process. An investigator who is independent of the research process and is not involved in its activities will be responsible for randomization. For this purpose, a randomization in blocks of 4 will be used using pre-coded sealed envelopes to conceal the allocation. This process will be carried out one week after signing the consent form and the initial assessment.

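### The between-arm comparison of weight and HbA1c uses no baseline adjustment, although both baselines are collected; with 15 per arm this costs precision, mainly for HbA1c

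*Combined protocol and SAP*

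**What the plan says.** The quantitative analysis plan is section 5.8.1 alone. After descriptive tabulation it compares the three arms on "the difference in weight (every 15 days for three months) and the difference in the percentage of glycated hemoglobin (at three months". The next sentence gives the effect measure: "For this purpose, relative risks with 95% confidence intervals will be used". It names no model, covariate or baseline term, and nor does any other section.

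The baseline values exist. Under Phase 1: Baseline (section 3.6.2): "Anthropometric measurements such as weight, height and blood pressure, and blood tests such as glycated hemoglobin (HbA1c) will also be included". Section 3.6.1 places randomisation after the initial assessment, so these values can serve as pre-randomisation covariates.

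The arms are small: "45 patients assigned to three intervention groups, 15 in each group" (section 3.4). Allocation is by "a randomization in blocks of 4 will be used using pre-coded sealed envelopes to conceal the allocation" (section 3.6.1), and no stratification by weight, BMI or HbA1c is mentioned. Eligibility (section 3.3.1) allows a BMI of 25 to 39.9 kg/m², described as a "range that includes from overweight to severe obesity", and sets no HbA1c limit. Baseline spread may therefore be wide.

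**The concern.** A change from baseline is usually negatively correlated with the baseline itself: patients who start higher tend to fall further. If one arm starts higher by chance, an unadjusted comparison of change credits part of that head start to the incentive type. Including the baseline value in the model removes this and reduces residual variance as well.

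Section 2 says the results will be used to design a later randomised trial, and section 4.12 plans publication. An arm that looks better only because of where it started could influence that design.

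**Working it through.** **The plan's own figures.** 3 × 15 = 45 agrees with section 3.4. No effect size, SD, power or dropout rate is given, so the sample size cannot be reproduced any further.

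**Inputs.** From the documents: 15 per arm, three arms, and an HbA1c goal of a fall of at least 1% (section 3.5). Assumed, because the documents give no figures: a pre-post correlation ρ of 0.5 to 0.7 for HbA1c, an HbA1c SD of 1.5 to 2.0 points, and equal SDs at the two times.

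**1. Chance imbalance at baseline.** The standard error of a difference in baseline means is SD × √(2/15) = 0.365 SD. The probability of a difference above 0.5 SD for a given pair of arms is 2 × [1 − Φ(0.5/0.365)] = 17%. For at least one of the three pairs it is 36% (by simulation).

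**2. How much of it reaches the result.** A raw change carries (1 − ρ) of the imbalance. For a 0.5 SD imbalance:

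| ρ | shift in the difference in mean change |
|---|---|
| 0.5 | 0.25 SD |
| 0.7 | 0.15 SD |
| 0.95 | 0.025 SD |
| 0.98 | 0.01 SD |

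In HbA1c points, the 95% limits of chance imbalance give shifts from 1.96 × 0.365 × 1.5 × (1 − 0.7) = 0.32 to 1.96 × 0.365 × 2.0 × (1 − 0.5) = 0.72.

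**3. Precision.** Per patient, the variance of change is 2s²(1 − ρ), and after baseline adjustment it is s²(1 − ρ²). The ratio is 2/(1 + ρ). Estimating the covariate slope multiplies the adjusted variance by about 1 + 1/40 = 1.025, since 45 − 3 = 42 within-arm degrees of freedom and 42 − 2 = 40. The net ratio is 2/(1 + ρ)/1.025, and the confidence interval width is multiplied by 1/√(net ratio).

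| ρ | gross ratio | net ratio | CI narrower by |
|---|---|---|---|
| 0.5 | 1.333 | 1.301 | 12% |
| 0.7 | 1.176 | 1.148 | 7% |
| 0.95 | 1.026 | 1.001 | 0% |
| 0.98 | 1.010 | 0.985 | slightly wider |

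A net ratio of 1.15 to 1.30 is equivalent to 15 to 30% more patients. Simulation with 20,000 runs per value agreed with the formula: 1.22 at ρ = 0.6 (formula 1.22), 1.00 at 0.95 and 0.985 at 0.98. Both estimators averaged to zero when there was no true effect.

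**4. If the outcome is yes/no.** The formulas in step 3 do not apply to a relative risk, but the dependence on baseline remains. Take an HbA1c fall of at least 1% as the outcome, with normality, the assumptions above, a mean fall of 0.3 to 1.0 points in every arm and no incentive effect. A 0.5 SD imbalance then gives expected responder proportions of about 31 to 55% in the higher-starting arm against 24 to 46% in the other, a relative risk of about 1.17 to 1.32. For scale, illustrative counts of 8/15 against 4/15 give a relative risk of 2.0 with 95% confidence interval 0.76 to 5.24.

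**The case against.** **The plan does not clearly compare mean changes.** A reader might infer from the outcome list alone that arms will be compared on mean raw change. The following sentence names relative risks, which need a yes/no outcome, and section 5.8.1 gives no cut-off. The only yes/no rules are for payment: the HbA1c fall of at least 1% and, for weight, "if they have managed to lose one kilogram in a two-week period" (section 3.5). The difference in weight could even mean change since the previous visit. This stands: outcome type and effect measure must be settled together, and the precision figures apply only to a continuous analysis. It does not remove the point. The named outcomes are continuous differences, and a responder version would still depend on the starting level.

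**Chance imbalance is not bias.** A reader might infer that the planned comparison is biased. It is not: averaged over randomisations, adjusted and unadjusted estimates are both unbiased, and a valid confidence interval already allows for chance imbalance. What remains is avoidable error in the one allocation that occurs, and a wider interval.

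**Weight gains little.** A reader might extend the precision loss to both outcomes. Three-month weight may correlate very highly with baseline weight, in which case subtracting baseline already does nearly all the work. This stands.

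**It is an exploratory pilot.** The general objective concerns implementation, there is no power claim, and section 2 does not say that the between-arm HbA1c difference will set the next trial's effect size. This limits the consequence. The plan nevertheless commits to between-arm comparisons with 95% confidence intervals.

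**Conclusion.** The point holds in a limited form. No baseline adjustment is specified, both baselines are available, and the arms are small with no stated stratification. For HbA1c analysed as continuous, adjustment narrows the confidence interval by about 7 to 12% and removes a possible shift of 0.32 to 0.72 points at the 95% limits of chance imbalance, against a goal of 1%. These figures rest on the assumed correlation and, for the shift in points, on the assumed SD. The imbalance probabilities of 17% and 36% rest only on 15 per arm, simple random allocation and approximate normality. For weight the gain is small, and nil at a correlation of about 0.95 or more.

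The documents do not support calling the planned analysis biased, or saying that precision is lost for both outcomes. The change should be made before results are seen, but its absence does not undermine the pilot's main purpose.

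**What to change.** In section 5.8.1:

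- For the two continuous outcomes, replace the relative risk with an adjusted mean difference between arms and its 95% confidence interval.
- **HbA1c at three months:** a linear model with arm and baseline HbA1c.
- **Repeated weights:** a mixed model with arm, visit, arm-by-visit interaction and baseline weight. State that the outcome is measured from baseline, not from the previous visit.
- Use the pre-randomisation baseline values. Say which weight reading this is, because section 3.5 also lists an initial weight assessment under each intervention.
- Keep raw change as description.
- If a yes/no goal is also reported, such as an HbA1c fall of at least 1%, define it, treat it as secondary, and note that it depends on the starting level.

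The baseline term costs one degree of freedom per model and no new data. The drafting cost is more than one sentence, because the effect measure changes and the repeated weights need their own model.
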